- Patient Global Impression of Change (PGIC) response at Week 4, Week 8, Week 12 respectively
- The achievement of subjects who are "Very much improved" or "Much improved" on the Patient Global Impression of Change (PGIC) at Week 4, Week 8, Week 12 respectively
- Change from baseline in PGIS at Week 4, Week 8, Week 12 respectively
- Occurrence of CD-related surgeries through Week 12
- The achievement of any reduction in SES-CD at Week 12
- The achievement of CDAI clinical remission at Week 4, Week 8, Week 12 respectively
- The achievement of CDAI clinical response at Week 4, Week 8, Week 12 respectively
- The achievement of SF remission at Week 4, Week 8, Week 12 respectively
- The achievement of AP remission at Week 4, Week 8, Week 12 respectively
- Change from baseline in CDAI at Week 4, Week 8, Week 12 respectively
- Change from baseline in Crohn's Symptom Severity (CSS) at Week 4, Week 8, Week 12 respectively
- The achievement of resolution of extra-intestinal manifestations (EIMs) at Week 4, Week 8, Week 12 respectively, in subjects with any EIMs at baseline
- The achievement of no draining fistulas at Week 4, Week 8, Week 12 respectively, in subjects with draining fistulas at baseline
- The achievement of no non-draining fistulas at Week 4, Week 8, Week 12 respectively, in subjects with non-draining fistulas at baseline

- The achievement of no anal fissure at Week 4, Week 8, Week 12 respectively, in subjects with anal fissure at baseline

Induction Period 2:

- The achievement of clinical remission at Week 16, 20, 24 respectively
- The achievement of endoscopic response at Week 24
- The achievement of CDAI clinical remission at Week 16, 20, 24 respectively
- The achievement of CDAI clinical response at Week 16, 20, 24 respectively
- The achievement of SF remission at Week 16, 20, 24 respectively
- The achievement of AP remission at Week 16, 20, 24 respectively
- Change from baseline in FACIT-Fatigue at Week 24
- Change from baseline in IBDQ total score at Week 24
- The achievement of enhanced clinical response and endoscopic response at Week 24
- The achievement of CDAI clinical response and endoscopic response at Week 24
- The achievement of endoscopic remission at Week 24
- The achievement of enhanced clinical response at Week 16, 20, 24 respectively
- The achievement of ulcer-free endoscopy at Week 24
- The achievement of resolution of extra-intestinal manifestations (EIMs) at Week 16, 20, 24 respectively, in subjects with any EIMs at baseline

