7.1 Demographics and Baseline Characteristics

The following demographic and baseline or disease characteristics will be summarized at the baseline of the study, where the baseline refers to the last non-missing observation before the first administration of any study drug.

Demographics

- Age (years)
- Age category [< 18 , [18, 40), [40, 65), ≥ 65]
- Sex [male/female]
- Race [American Indian/Alaska Native, Asian, Black or African American, Native Hawaiian or Other Pacific Islander, White, Multiple]
- Ethnicity [Hispanic/Latino, Non-Hispanic/Latino]
- Geographic region (as defined in [Appendix I](#))

Tobacco/Nicotine and Alcohol Use

- Tobacco/Nicotine Use [currently smokes, ex-smoker, never smoked, unknown]
- Alcohol Use [current drinker, former drinker, non-drinker, unknown]

Vital Signs

- Systolic and diastolic blood pressure (mmHg)
- Pulse (bpm)
- Body temperature (°C)
- Body weight (kg) – overall and by sex
- Body weight category (< 60 kg, ≥ 60 kg)
- Height (cm)
- Body Mass Index (kg/m²)
- BMI Category
 - Underweight [< 18.5 kg/m²]
 - Normal [≥ 18.5 and < 25 kg/m²]
 - Overweight [≥ 25 and < 30 kg/m²]
 - Obese [≥ 30 kg/m²]

Patient Reported Outcomes at Baseline

- IBDQ – total score and domain scores
- WPAI-CD – 4 sub-scores
- CSS – total score
- FACIT-Fatigue – total score and 13 item scores
- EQ-5D-5L – Index score and Vas Pain
- SF-36 – 8 domain scores, PCS and MCS
- Average Daily Stool Frequency
- Average Daily Abdominal Pain

Other Assessments at Baseline

- CDAI
- SES-CD
- Crohn's Disease Duration (years)
- Fecal calprotectin
- Baseline corticosteroid use (yes, no)
- Baseline immunomodulator use (yes, no)
- Biologics failure history (0, 1, >1)
- TNF failure history (0, 1, >1) within bio-IR population
- Vedolizumab failure history (yes, no) within bio-IR population
- Ustekinumab failure history (yes, no) within bio-IR population
- hs-CRP
- Draining fistulas (yes, no)
- Non-draining fistulas (yes, no)
- Anal fissures (yes, no)
- Crohn's Disease Location Per SES-CD (colonic only, ileal only, ileal-colonic)
- Extra Intestinal Manifestation (yes, no)

In addition, some clinical tests at baseline such as TB test, pregnancy test and electrocardiogram assessment will be summarized. Crohn's Disease history (Montreal classification) and Crohn's Disease surgical history will be summarized separately as well.

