8.2 Handling of Potential Intercurrent Events

Potential intercurrent events considered in this study include 1) premature discontinuation of study drug and 2) initiation or dose escalation of CD-related corticosteroids defined in Section 8.2.2. Intercurrent events will be handled using the following methods for the efficacy analysis:

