8.6 Additional Efficacy Analyses

Other continuous and categorical efficacy endpoints for the 12-Week Induction Period will be analyzed using ITT1A similarly as the secondary efficacy endpoints as described in Section 8.5. No multiplicity adjustment will be performed. The chi-square test (or Fisher's exact test if $\geq 20\%$ of the cells have expected cell count < 5 for analyses of binary outcomes) will be used for the following endpoints:

- Patient Global Impression of Severity (PGIS) response at Week 4, Week 8, Week 12 respectively
- Patient Global Impression of Change (PGIC) response at Week 4, Week 8, Week 12 respectively
- The achievement of no draining fistulas at Week 4, Week 8, Week 12 respectively, in subjects with draining fistulas at baseline
- The achievement of no non-draining fistulas at Week 4, Week 8, Week 12 respectively, in subjects with non-draining fistulas at baseline

- The achievement of no anal fissure at Week 4, Week 8, Week 12 respectively, in subjects with anal fissure at baseline

PGIC response and PGIS response endpoints will be analyzed based on the observed data using AO approach. The draining fistulas endpoint, non-draining fistulas endpoint and anal fissure endpoint will be analyzed using NRI-NC approach due to the small sample size.

Analyses for other efficacy endpoints as specified in Section 3.3 for Induction Period 2 will be performed using ITT2A for exploratory purpose. Point estimate and 95% CI for each treatment group as well as point estimate and 95% CI for pairwise treatment differences (i.e., risankizumab 1200mg IV – risankizumab 360mg SC, risankizumab 1200mg IV – risankizumab 180mg SC, risankizumab 360mg SC - risankizumab 180mg SC) will be presented based on the observed data for randomized subjects using AO approach. The subjects in the non-randomized risankizumab 1200mg IV group, who took the placebo in the 12-Week Induction Period, will be displayed separately using descriptive statistics. No p-value will be provided.

In addition, the following selected endpoints will be analyzed using ITT1B for exploratory purpose. Point estimate and 95% CI for each treatment group as well as point estimate and 95% CI for treatment differences between each risankizumab group and the placebo group will be presented based on the observed data using AO approach. No p-value will be provided.

- The achievement of CDAI clinical remission at Week 12
- The achievement of clinical remission at Week 12

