Appendix D. Crohn's Disease Activity Index (CDAI)

The Crohn's Disease Activity Index (CDAI) is a composite instrument that includes patient symptoms evaluated over 7 days (abdominal pain, stool frequency and general well-being), as well as physical and laboratory findings. These items are scored individually, weighted, and do not contribute equally to the overall score. The CDAI is derived from summing up the weighted individual scores of eight items as outlined below:

| | | | Factor | Subtotal |
|--|---|---|--------|----------|
| 1. Number of liquid or very soft stools (Record the frequency per day) | $\frac{_ + _ + _ + _ + _ + _ + _}{\text{Days: 1 2 3 4 5 6 7 Sum}} = \frac{_}{_}$ | × | 2 | |
| 2. Abdominal pain rating: 0 = none, 1 = mild, 2 = moderate, 3 = severe | $\frac{_ + _ + _ + _ + _ + _ + _}{\text{Days: 1 2 3 4 5 6 7 Sum}} = \frac{_}{_}$ | × | 5 | |
| 3. General well-being: 0 = generally well, 1 = slightly underpar, 2 = poor, 3 = very poor, 4 = terrible | $\frac{_ + _ + _ + _ + _ + _ + _}{\text{Days: 1 2 3 4 5 6 7 Sum}} = \frac{_}{_}$ | × | 7 | |
| 4. Number of 6 listed categories the subject now has Check all items that apply:  Arthritis/arthralgia  Iritis/uveitis  Erythema nodosum/pyoderma gangrenosum/aphthous stomatitis  Fissure, abscess and/or anal fistula (draining/non-draining)  Other cutaneous fistula (draining/non-draining) Fistula  Fever over 100°F (37.8°C) during past week | _____ _____ Record "0" if no categories checked | × | 20 | |
| 5. Taking Lomotil/Imodium/Loperamide/opiates for diarrhea 0 = no, 1 = yes | _____ | × | 30 | |
| 6. Abdominal mass 0 = none, 2 = questionable, 5 = defined | _____ | × | 10 | |
| 7. Hematocrit: ____. | Male: (47 – hematocrit) = _____ Female: (42 – hematocrit) = _____ Subtotal If hematocrit > normal, enter "0" | × | 6 | |

| | | | Factor | Subtotal |
|---|---|---|---------------|-----------------|
| 8. Body weight: _____.__(kg) Standard weight: _____.__(kg) | $100 \times [1 - (\text{Body wt}/\text{Standard wt})] =$ Percent below standard weight: _____ If body wt > std. wt, enter "0" | × | 1 | |
| | | | Total | |

CDAI with higher score indicates more severe disease. For the calculation of CDAI and components at each visit, the following rules will be applied:

- The 7 most recent useable days out of the 14 days preceding the visit will be used.

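### As worded, the non-draining fistula endpoint counts a subject whose non-draining fistula has started to drain as a responder

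*SAP*

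**What the plan says.** SAP Section 3.3 includes, among the other efficacy endpoints of the 12-Week Induction Period, "The achievement of no non-draining fistulas at Week 4, Week 8, Week 12 respectively, in subjects with non-draining fistulas at baseline". Its companion is "The achievement of no draining fistulas at Week 4, Week 8, Week 12 respectively, in subjects with draining fistulas at baseline". Each endpoint has its own denominator, fixed by baseline status. Section 7.1 treats draining and non-draining fistulas as two separate yes/no baseline characteristics.

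Section 8.6 assigns the endpoint a chi-square test (or Fisher's exact test when expected counts are small) and sets the missing-data rule: "The draining fistulas endpoint, non-draining fistulas endpoint and anal fissure endpoint will be analyzed using NRI-NC approach due to the small sample size". On error control the same section says "No multiplicity adjustment will be performed"; Section 8.1 places such endpoints at a nominal two-sided 0.05. Section 8.2 limits the intercurrent events: "Potential intercurrent events considered in this study include 1) premature discontinuation of study drug and 2) initiation or dose escalation of CD-related corticosteroids". Section 12.0 records that the non-draining fistula endpoint was added in the current version of the SAP because of its clinical importance.

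**The concern.** The endpoint is evidently meant to measure resolution of non-draining fistulas, but the condition it tests is absence of the non-draining state. A fistula can leave that state by closing or by starting to drain. The first is an improvement and the second a deterioration, and the wording credits both.

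A response rate that mixes the two cannot be read as a healing rate in either arm. The denominator is also likely to be small, since Section 8.6 gives small sample size as its reason for choosing NRI-NC, so one or two such subjects could visibly change the reported percentages.

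**Working it through.** The SAP states no rate, sample size or power for this endpoint, so there is no figure to reproduce. The check is of the definition, followed by arithmetic on assumed rates.

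**Step 1: trace each visit state.** Take a subject with one non-draining fistula and no draining fistula at baseline.

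| State at the visit | Non-draining fistula present? | Scored as | Matches clinical direction? |
|---|---|---|---|
| Closed | No | Responder | Yes |
| Still non-draining | Yes | Non-responder | Yes |
| Now draining | No | Responder | No, the subject is worse |
| Missing | Unknown | Non-responder (NRI-NC) | Conservative by design |

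**Step 2: look for a rule that overrides the third row.**
- Section 3.0 has no separate definition of this endpoint, so the Section 3.3 wording governs.
- NRI-NC (Section 8.3.1) turns missing data into non-response. An observed conversion is not missing.
- Section 8.2 names only study drug discontinuation and CD-related corticosteroids. Conversion to draining is neither.
- The draining-fistula endpoint counts only subjects draining at baseline, so this subject is outside it.
- CDAI item 4 (Appendix D) puts draining and non-draining fistulas in the same tick-box category, so conversion alone leaves that item unchanged.

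Nothing in the SAP scores the third row as failure.

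**Step 3: weight of one conversion.** Group sizes are those in Section 2.4: 171 placebo and 342 per risankizumab dose. (The list in Section 2.2 gives 342 for placebo and 171 for 1200 mg; Section 2.4 is used here.) Assume 5-10% of ITT1A had a non-draining fistula at baseline.
- Placebo: 0.05 × 171 ≈ 9 to 0.10 × 171 ≈ 17 subjects. One conversion is 1/17 = 5.9 to 1/9 = 11.1 percentage points.
- Each risankizumab dose: 0.05 × 342 ≈ 17 to 0.10 × 342 ≈ 34 subjects. One conversion is 1/34 = 2.9 to 1/17 = 5.9 percentage points.

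**Step 4: effect on the treatment difference.** With one fistula per subject, let c be the closure rate and d the rate of conversion to draining, with subscript R for risankizumab and P for placebo.

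Difference as written = (c_R + d_R) − (c_P + d_P) = (c_R − c_P) + (d_R − d_P).

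The distortion is therefore d_R − d_P. Assume closure of 25% against 15%, a closure difference of +10 points throughout:

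| d_R | d_P | Difference as written | Conversions among placebo responders |
|---|---|---|---|
| 5% | 5% | 30 − 20 = +10 | 5/20 = 25% |
| 5% | 10% | 30 − 25 = +5 | 10/25 = 40% |
| 5% | 15% | 30 − 30 = 0 | 15/30 = 50% |
| 5% | 20% | 30 − 35 = −5 | 20/35 = 57% |
| 10% | 5% | 35 − 20 = +15 | 5/20 = 25% |

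All these rates are assumed. The last row shows that the sign of the distortion depends on which arm has more conversions, which the SAP does not say.

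**The case against.** The strongest case against is that little depends on this endpoint and that several rules limit which converters are counted. Most of that stands.

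- The endpoint is neither co-primary nor ranked. The ranked fistula endpoint concerns draining fistulas; moving from draining to non-draining is an improvement, so it does not share the fault.
- A reader might infer that every conversion is a false success. It is not. A subject with several non-draining fistulas responds only if all have closed or converted. One who misses the visit is a non-responder. One who starts or escalates CD-related corticosteroids at or before the visit is counted as a non-responder (Sections 8.2.2 and 8.3.1). These safeguards are partial, and the steroid rule does not apply in an as-observed analysis (Section 8.3.2).
- A reader might infer that the draining-fistula endpoint never sees the worsening. A subject with both types at baseline is in that denominator, and a newly draining tract makes that subject a failure there. The gap is for those with none draining at baseline.
- A reader might infer that conversion is commoner on placebo, so the comparison is biased against risankizumab. Conversion of 10% against 3% would give 7 points. The SAP supports neither the direction nor the rates. On the denominators above, 10% of 9-17 is 0.9-1.7 placebo subjects and 3% of 17-34 is 0.5-1.0 risankizumab subjects, or about one per arm. With an assumed 20% response in both arms, the 95% half-width for the difference is 1.96 × √(0.16/17 + 0.16/34) ≈ 23 points to 1.96 × √(0.16/9 + 0.16/17) ≈ 32 points. The endpoint is imprecise in any case.
- The SAP does not say in words that converters are responders, and it does not show whether fistulas are tracked individually. The conclusion follows from the definition and the absence of any exclusion.

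None of this changes the third row of the state table. It limits the consequence.

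**Conclusion.** The point holds as a fault of definition. In Sections 3.3 and 8.6, a subject whose only or every remaining non-draining fistula has started to drain is scored as a responder. If none was draining at baseline, no fistula endpoint records the worsening.

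The fault affects one other efficacy endpoint, in the 12-Week Induction Period only. Co-primary results, ranked secondary results and sample size are untouched. The per-conversion shifts calculated above rest on the assumed 5-10% prevalence, and the net effect on the treatment difference cannot be sized or signed from the SAP. A claim of known bias toward either arm would go beyond the document. It merits correction because the definition rewards deterioration in a newly added endpoint that will be tested between arms, and because the correction is cheap.

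**What to change.** In Sections 3.3 and 8.6, state that a subject with non-draining fistulas at baseline is a responder at a visit only if no non-draining fistula is present and none of the baseline non-draining fistulas has become draining. If fistulas are recorded only as present or absent, add instead that a subject with no draining fistula at baseline must also have none at the visit.

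A blanket requirement of no fistula of either kind would be too broad. It would fail a subject with both types at baseline whose non-draining fistula closed while the original draining one persisted.

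The cost is one sentence in the SAP and one programming condition. Draining status at Weeks 4, 8 and 12 is already needed for the draining-fistula endpoint. The CDAI form should not be cited as its source, because as printed in Appendix D its fistula boxes pool the two states. NRI-NC and the planned chi-square or Fisher's exact test stay unchanged.

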3.4 Safety Endpoint(s)

- Treatment-emergent adverse event
- Laboratory data
- Vital signs

3.5 Additional Endpoint(s)

Pharmacokinetics/pharmacodynamics, pharmacogenetics, and selected biomarkers will be analyzed separately and are not included in this SAP.

4.0 Analysis Populations

The following population sets are defined and will be used for the statistical analyses.

Significant non-compliance was identified at an investigational site (Investigator ID [REDACTED]). As a result of this finding, efficacy data for the subjects enrolled at this investigational site will be excluded from the statistical analyses. Safety data for those subjects will be included in the statistical analyses. There were 5 subjects enrolled at the site with Investigator ID [REDACTED] in this study.

Intent-to-Treat Population

The Intent-to-Treat (ITT) population includes subjects who received at least one dose of study drug.

12-Week Induction Period:

The Intent-to-Treat population for the 12-Week Induction Period (denoted as ITT1) includes randomized subjects who received at least one dose of study drug during the 12-Week Induction Period.

- **ITT1A:** This Intent-to-Treat population for the 12-Week Induction Period includes the subjects in ITT1 who had baseline eligible SES-CD of ≥ 6 (≥ 4 for

isolated ileal disease). This population will be the primary population for efficacy analysis of the 12-Week Induction Period.

- **ITT1B:** This Intent-to-Treat population for the 12-Week Induction Period includes the subjects who are in ITT1 set but did not have baseline eligible SES-CD of ≥ 6 (≥ 4 for isolated ileal disease). This population will be used for exploratory efficacy analysis purpose.

Induction Period 2:

The Intent-to-Treat population for the Induction Period 2 (denoted as ITT2) includes subjects who are randomized and received at least one dose of risankizumab during the Induction Period 2, and the subjects who received placebo induction treatment during 12-Week Induction Period and entered the Induction Period 2 (denoted as placebo/risankizumab). The placebo/risankizumab subjects will be analyzed as a separate treatment group in the Induction Period 2.

- **ITT2A:** This Intent-to-Treat population for Induction Period 2 includes subjects in ITT2 who had baseline eligible SES-CD of ≥ 6 (≥ 4 for isolated ileal disease). This population will be used for exploratory efficacy analysis purpose.
- **ITT2B:** This Intent-to-Treat population for Induction Period 2 includes the subjects who are in ITT2 set but did not have baseline eligible SES-CD of ≥ 6 (≥ 4 for isolated ileal disease). This population will be used for exploratory efficacy analysis purpose.

For the corresponding ITT populations, subjects were assigned to a treatment group based on the randomization or re-randomization schedule, regardless of the treatment actually received. The demographics/baseline and efficacy analysis will be based on the corresponding ITT population.

Safety Population

For the safety populations, subjects were assigned to a treatment group based on the treatment actually received. The safety population (SA) consists of all subjects who received at least one dose of study medication. The safety analysis in each induction period will be based on the following safety population.

12-Week Induction Period:

- **SA1:** This safety population for the 12-Week Induction Period consists of all subjects who received at least one dose of study medication from the 12-Week Induction Period.
- **SA1A:** This safety population for the 12-Week Induction Period includes the subjects in SA1 set who had baseline eligible SES-CD of ≥ 6 (≥ 4 for isolated ileal disease).

Induction Period 2:

- **SA2:** This safety population for the Induction Period 2 consists of subjects who received at least one dose of risankizumab during the Induction Period 2.
- **SA2A:** This safety population for the Induction Period 2 includes the subjects in SA2 set who had baseline eligible SES-CD of ≥ 6 (≥ 4 for isolated ileal disease).

All Risankizumab:

- **SA-ALL:** This safety population includes all subjects who received at least one dose of risankizumab any time during the study.

5.0 Subject Disposition

The total number of subjects who were enrolled, randomized and treated will be summarized.

A summary of subject accountability will be provided where the number of subjects in each of the following categories will be summarized for each treatment group:

- Subjects enrolled/randomized in the study
- Subjects who took at least one dose of study drug (ITT1A for the 12-Week Induction Period, ITT2 for the Induction Period 2 and ITT1 for the entire study)
- Subjects who completed study drug (SA1A for the 12-Week Induction Period, SA2 for the Induction Period 2 and SA1 for the entire study)
- Subjects who prematurely discontinued study drug (SA1A for the 12-Week Induction Period, SA2 for the Induction Period 2 and SA1 for the entire study)
- Subjects who prematurely discontinued from study (ITT1A for the 12-Week Induction Period, ITT2 for the Induction Period 2 and ITT1 for the entire study)
- Subjects who completed study (ITT1A for the 12-Week Induction Period, ITT2 for the Induction Period 2 and ITT1 for the entire study)

For end of study participation, the number and percentage of subjects who completed the protocol defined follow-up period (or did not with associated reasons) will be summarized overall and by treatment group.

